5.3. Power and Sample Size Calculations

Approximately 270 participants will be randomized (2:1:2) to receive placebo, 0.3 mg JZP150, or 4 mg JZP150.

The sample size was determined based on ensuring at least 80% marginal power to detect a difference of 6 between placebo and each dose of JZP150 for the change in CAPS-5 total score from Baseline to Week 12 ([Stefanovics et al 2018](#); [Stein et al 2006](#)). The sample size for the estimated 70% of evaluable participants completing the 12-week dosing period for each arm (placebo [$n = 75$], 0.3 mg JZP150 [$n = 38$], and 4 mg JZP150 [$n = 75$]) provides a marginal power of 93.4% and 80.9% for comparing the high dose vs placebo and low dose vs placebo, respectively. Calculations are based on assuming a common standard deviation of 10.5, using a two-sample t-test, and two-sided significance level of 0.05. To account for a 30% dropout, a total of 270 participants will be randomized to ensure that a minimum of 188 participants have 12 weeks of intervention data.

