6. ANALYSIS SETS

For purposes of analysis, the following populations are defined in Table 2.

Table 2: Analysis Sets

Analysis Set	Description
Enrolled Analysis Set	The Enrolled Analysis Set includes all participants who provided a signed ICF. This analysis set will be used to summarize participant disposition including number of screened, screen failures, and randomized participants.
Full Analysis Set 1	The Full Analysis Set 1 includes all participants who were randomized and took at least 1 dose of the study intervention, excluding Site 1865*. This analysis set will be the primary analysis set for all efficacy analyses. This analysis set will also be used in the concordance analysis to examine the classification of participants in randomization strata according to different data sources. Participants will be summarized according to the treatment group they were randomized to.
Full Analysis Set 2	The Full Analysis Set 2 includes all participants who were randomized and took at least 1 dose of the study intervention. This analysis set will be used to summarize participant disposition and protocol deviations. This analysis set will also be used in supplementary efficacy analysis. Participants will be summarized according to the treatment group they were randomized to.
Safety Analysis Set	The Safety Analysis Set includes all participants who took at least 1 dose of study intervention. This analysis set will be used to summarize participants' demographic and other baseline characteristics data, past medical conditions/diseases, surgical history, medications, PTSD diagnosis history, exposure to study

Jazz Pharmaceuticals
 {Statistical Analysis Plan - Protocol #}JZP150-201-02

Analysis Set	Description
	intervention, as well as all safety data. Participants will be summarized according to the study intervention they actually received.
Modified Full Analysis Set	The Modified Full Analysis Set includes all participants in the Full Analysis Set 1 who have baseline and at least 1 post-baseline assessment of CAPS-5 total score, CGI-S, or PGI-S score, excluding ineligible participants that were randomized. This analysis set will be used in supplementary efficacy analysis. Participants will be summarized according to the treatment group they were randomized to.

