10.2. Adverse Events

Adverse events (AEs) occurring from the first dose of study intervention until the final study visit will be reported. If the Investigator becomes aware of an SAE within 14 days after the last dose of study intervention, the event must also be reported. In addition, any SAE assessed as related to study intervention or procedure by the Investigator must be reported regardless of time after study termination.

Adverse events will be coded to SOC and PT using MedDRA, Version 24.0 or later. The investigator will assess the relationship of each AE to study intervention. An AE with a missing relationship to study intervention will be reported as related in the summaries. Severity, as determined by the Investigator, will be classed as mild, moderate, severe, life-threatening, or fatal.

Note that participants who acquire COVID-19 or report AEs due to the COVID-19 public health emergency (e.g., anxiety) while on study will be coded accordingly and included in the treatment emergent adverse event (TEAE) summaries.

Jazz Pharmaceuticals
 {Statistical Analysis Plan - Protocol #}JZP150-201-02

A TEAE is generally defined as any event with onset date on or after the first dose of study intervention, including AEs that occur until 14 days after the last dose date. Any AEs reported 14 days after the last dose date will not be considered treatment emergent and will be included in the listing but not analyzed in the summaries.

For the purpose of calculating treatment emergence, incomplete onset dates will be imputed as detailed in [Appendix 2](#).

For the summary of TEAEs in Safety Analysis Set by time of first onset, data will be summarized under the following categories:

- Week 1 (Day 1 to 7).
- Weeks 2 to 4 (Day 8 to 28).
- Weeks 5 to 8 (Day 29 to 56).
- Weeks 9 to 12 (Day 57 to 84).
- After last dose.

The time of first onset will be calculated for TEAEs as:

$$\text{Start date of TEAE} - \text{Date of first dose of study intervention} + 1 \text{ day}$$

If patients have multiple occurrences of a TEAE then it will be counted once for the first occurrence only. For participants who discontinue study intervention prior to study completion, all TEAEs occurring after treatment discontinuation will be reported in the “After last dose” category.

The time of first onset will also be used to assign TEAEs by study period onset as follows:

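### SAP 10.2's table of TEAEs by time of first onset counts only on-drug events in its week bands but sets no at-risk denominator, so late-band incidence would read low on the plain reading

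*SAP*

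**What the plan says.** The summary by time of first onset is set up in SAP 10.2: "For the summary of TEAEs in Safety Analysis Set by time of first onset, data will be summarized under the following categories". The categories are Week 1 (Days 1-7), Weeks 2-4 (Days 8-28), Weeks 5-8 (Days 29-56), Weeks 9-12 (Days 57-84) and a final category for events after the last dose. Two rules govern the count. First, "If patients have multiple occurrences of a TEAE then it will be counted once for the first occurrence only". Second, "For participants who discontinue study intervention prior to study completion, all TEAEs occurring after treatment discontinuation will be reported in the" after-last-dose category.

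SAP 6 defines the population: "The Safety Analysis Set includes all participants who took at least 1 dose of study intervention". SAP 10.2 lists the table among its participant-incidence summaries by SOC and PT. It specifies no number at risk per band, exposure-adjusted rate or time-to-event estimate for adverse events. On attrition, SAP 5.3 plans on an "estimated 70% of evaluable participants completing the 12-week dosing period for each arm".

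**The concern.** Once a participant stops study intervention, nothing that happens to them can enter a later week band, yet they remain in the Safety Analysis Set. If percentages are taken over that whole set, the later bands divide on-drug events by a group that includes people no longer on drug. A steady risk would then look lower late in treatment and could be read as tolerance. If discontinuation differs between arms, the arm losing more people would look safer in the late bands.

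This matters more than usual here. Protocol 2.2 describes a 28-day study as the longest of the investigator-initiated studies, and Protocol 4.3 reports repeated 4 mg dosing for up to 30 days. Apart from a possible Day 29-30 overlap, the last two bands therefore cover longer 4 mg exposure than those sections report. Protocol 2.1 says the results will inform the design and dose selection of later studies.

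**Working it through.** **Plan's own figure.** The documents state no TEAE incidence by band. The figure that drives the calculation is the 30% dropout: 188/(1 - 0.30) = 268.6, or 269, against about 270 stated in SAP 5.3. With 2:1:2 allocation the arms are 108, 54 and 108.

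**Assumptions not in the documents.** Constant first-onset hazard λ; discontinuation independent of event risk; several dropout patterns, each leaving 70% on drug at Day 84. Risk is set at 10% per 28 days, so λ = -ln(0.9)/28 per day.

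**Formula on the whole-set reading.** Band incidence = ∫ λ·exp(-λt)·S(t) dt over the band, where S(t) is the share still on drug. Understatement = 1 - (this value)/(the same integral with S = 1).

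**No dropout.** Weeks 5-8: 0.90 - 0.81 = 9.0%. Weeks 9-12: 0.81 - 0.729 = 8.1%. This fall comes from first-occurrence counting alone.

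**30% dropout.**

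| Pattern | Weeks 5-8 | Weeks 9-12 | Understatement |
|---|---|---|---|
| Constant rate | 7.5% | 6.0% | 16%, 26% |
| Linear | 7.7% | 6.1% | 15%, 25% |
| All by Day 28 | 6.3% | 5.7% | 30%, 30% |
| All after Day 56 | 9.0% | 6.9% | 0%, 15% |

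The understatement is close to one minus the mean share on drug in the band. For the constant rate, S(t) = 0.7^(t/84) averages 0.837 over Weeks 5-8 and 0.743 over Weeks 9-12. At 5% risk per 28 days the constant-rate bands read 4.0% and 3.4%, again falling.

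**Per 7 days.** Constant rate, 10% risk: 2.6, 2.3, 1.9 and 1.5% across the four bands, under a hazard that does not change.

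**Unequal dropout (assumed).** With 25% v 35% at constant rates, the mean share on drug in Weeks 9-12 is 0.786 v 0.697. The ratio is 0.697/0.786 = 0.887, so equal risk looks about 11% lower in the arm with more dropout. With 20% v 40%, Weeks 9-12 reads 6.7% v 5.3%.

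**Candidate denominators (constant rate, 10% risk).**
- On drug at band start: 8.5% then 7.6%. A false decline remains.
- On drug and event-free at band start: 9.4% in both bands.
- Events per 100 on-drug person-weeks, not censored at first event: 2.60, 2.47, 2.25, 2.03. Still falling.
- The same rate, censored at first event or last dose: -ln(0.9)/4 = 2.63 per 100 person-weeks in every band.

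If all dropout falls after Day 56, the event-free denominator gives 10.0% then 8.5%, because people leave within the band. The censored rate stays at 2.63.

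**The case against.** The strongest reply is that the SAP never states this table's percentage denominator. It names a population and a list of categories. Where it wants to fix a denominator it does so, as in SAP 8.3 for baseline tables and SAP 10.6.1 for physical-examination shifts. A reader might infer that the SAP prescribes the whole-set denominator; the text does not go that far. It is the plain reading, and the wording needs settling whichever denominator was meant.

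Four other stronger readings also fail:
- **Incidence would fall steadily from Week 1.** The bands last 7, 21, 28 and 28 days. In the constant-rate example the raw figures are 2.6, 6.9, 7.5 and 6.0%, so the false decline shows only between the two equal bands and in per-week terms.
- **All of the fall is due to dropout.** Part is first-occurrence counting (9.0% to 8.1% with no dropout).
- **No other output shows when events start.** SAP 10.2 also plans TEAEs by study period and a listing of all AEs. Discontinuation by arm (SAP 8.2) and exposure duration (SAP 10.1.1) are reported too, so attrition is not hidden. None of these gives onset incidence by week or a number at risk.
- **No JZP150 dosing had gone beyond 28 days.** Protocol 4.3 reports 4 mg for up to 30 days.

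One might also cite the later sentence in SAP 10.2 that assigns post-discontinuation TEAEs by time of first onset. It belongs to the study-period split, which has no week bands. Even if applied here it would add little: treatment emergence ends 14 days after the last dose, so someone stopping at Day 28 could contribute only to Day 42.

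Finally, Protocol 9.4.5 makes safety analyses descriptive, without formal testing. That stands and limits the consequence to interpretation.

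**Conclusion.** The point holds as a gap in the specification of one descriptive table. The numerator is restricted to on-drug first onsets and no matching denominator is written. On the whole-set reading, with 30% discontinuing and constant risk, Weeks 9-12 incidence is understated by about 15-30% and Weeks 5-8 by 0-30%. Under an assumed constant dropout rate the figures are 26% and 16%. The distortion between arms is about 11% if dropout is 25% v 35%, which is an assumption; the plan expects the same completion in every arm. Dropout timing, the true hazard and independence of dropout from risk are all assumed. Overall TEAE incidence is not affected. This is a cheap improvement worth making, not a flaw in the main safety analysis.

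**What to change.** For the by-onset table only:
- Use as denominator the participants still on study intervention and without a prior occurrence of that TEAE at the start of each category (Days 1, 8, 29 and 57).
- Print the number on drug at the start of each band in the column head.
- Add first-onset events per 100 person-weeks on drug, with time censored at first event or last dose. This handles unequal band lengths and dropout within a band.
- For the after-last-dose category, use participants with any safety contact after their last dose.

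Keep the Safety Analysis Set denominator for the overall TEAE tables.

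The cost is a short SAP wording change and reprogramming of one table, using dose and event dates already needed for exposure and onset. The downside is that band percentages no longer sum to overall incidence and denominators vary by term, so a footnote is needed.

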9.4.5. Safety Analyses

All safety analyses will be made on the Safety Population. All safety analyses will be descriptive; no formal statistical testing will be performed and are further described in the SAP.

Adverse Event Analyses:

Adverse events will be mapped to system organ classes (SOC) and preferred terms using the Medical Dictionary for Regulatory Activities (MedDRA). The participant incidence of AEs, AEs related to study intervention, SAEs, AEs leading to discontinuation, and fatal AEs will be summarized. This overall summary will also provide AEs by maximum severity.

The participant incidence of AEs, AEs related to study intervention, AEs, and AEs leading to discontinuation will also be presented by SOC and preferred term (PT). Preferred term summaries may also be provided.

The participant incidence of an AE will be summarized; if a participant has multiple events with the same PT occurring in different periods, the event will be reported for each of those periods. If an AE continues from one period to the next without increase in severity, the event will be reported only for the period of the AE onset. Changes in the severity of an AE within a period will only be counted as one AE with the worst severity.

Vital Signs:

For each vital sign parameter, summary statistics will be provided for observed and change from baseline values by scheduled visit.

Physical Examinations:

Observed and change from baseline values for weight will be summarized descriptively by scheduled visit.

12-lead ECG:

Observed and change from baseline values for ECG intervals will be summarized descriptively. The number and percent of participants with values or change from baseline values in QT/QTcF exceeding certain thresholds will be tabulated.

Clinical Laboratory Evaluations:

Observed and change from baseline laboratory evaluations will be summarized descriptively.

C-SSRS:

Columbia Suicide Severity Ratio Scale parameters will be summarized by scheduled visit.

Marijuana Withdrawal Checklist

Marijuana Withdrawal Checklist parameters will be summarized by scheduled visit.

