
* These categories are based on the National Cancer Institute Common Terminology Criteria for Adverse Events version 5.0 or higher.
 
When the severity of an AE increases over time, the increase in the severity will be recorded as a new AE and the original AE will stop when the new AE starts.
 
An event is defined as ‘serious’ when it meets at least 1 of the predefined outcomes as described in the definition of an SAE, NOT when it is rated as severe.

Assessment of Causality

The investigator is obligated to assess the relationship between study intervention and each occurrence of each AE/SAE.A “reasonable possibility” of a relationship conveys that there are facts, evidence, and/or arguments to suggest a causal relationship, rather than a relationship, cannot be ruled out.The investigator will use clinical judgment to determine the relationship.Alternative causes, such as underlying disease(s), concomitant therapy, and other risk factors, as well as the temporal relationship of the event to study intervention administration, will be considered and investigated.The investigator will also consult the Investigator’s Brochure (IB) and/or Product Information, for marketed products, in his/her assessment.

Assessment of Causality

- For each AE/SAE, the investigator must document in the medical notes that he/she has reviewed the AE/SAE and has provided an assessment of causality.
- There may be situations in which an SAE has occurred and the investigator has minimal information to include in the initial report to the sponsor or designee. However, it is very important that the investigator always make an assessment of causality for every event before the initial transmission of the SAE data to the sponsor or designee.
- The investigator may change his/her opinion of causality in light of follow-up information and send an SAE follow-up report with the updated causality assessment.
- The causality assessment is one of the criteria used when determining regulatory reporting requirements.

Follow-up of AEs and SAEs

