- Intervention Period (Day 1 to Day 84 for intervention completers or Day 1 to last dosing day for participants who discontinue intervention early)
- Safety Follow-up Period (> Day 84 for intervention completers or > last dosing day for participants who discontinue intervention early)

If patients have multiple occurrences of a TEAE then it will be counted once for the first occurrence only. For participants who discontinue study intervention prior to study completion, TEAEs occurring after treatment discontinuation will be reported according to the time of first onset.

Only TEAEs are included in summary tables unless otherwise specified. If a participant has multiple episodes of events coded to the same SOC or PT, then the participant will be counted just once in the summaries for that term. For summary tables, participant incidence of TEAEs by SOC and PT are sorted by descending order of frequency of SOC in the JZP150 4 mg treatment arm (then alphabetically for ties) and then by descending order of frequency of PTs within each SOC (then alphabetically for ties). For summaries by PT only, PTs will be sorted in descending order of frequency in the JZP150 4 mg treatment arm. Each TEAE will be summarized by treatment group and pooled JZP150 treatment groups.

For the summary of TEAEs by maximal severity, for each participant, the worst severity recorded by PT and SOC will be used for summary purposes. If severity is missing, the severity level of “severe” will be assumed.

Jazz Pharmaceuticals
{Statistical Analysis Plan - Protocol #}JZP150-201-02

A general overall summary of TEAEs with the number and percent of participants who experienced the following types of events will be provided by treatment group and pooled JZP150 treatment groups:

- Participants with any TEAE
- Participants with any treatment-related TEAE
- Participants with any serious TEAE
- Participants with any treatment-related serious TEAE
- Participants with TEAE by maximum severity
- Participants with an AE outcome as death
- Participants with any TEAE leading to study intervention discontinuation
- Participants with any TEAE leading to study intervention dose interruption
- Participants with at least one TEAE outcome

Participant incidence of TEAEs by SOC and PT will be summarized by treatment group and pooled JZP150 treatment groups for the following:

- TEAEs (by SOC and PT and PT only)
- TEAEs reported in $\geq 2\%$ of participants
- Treatment-related TEAEs
- Serious TEAEs

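### SAP 10.2 counts a repeated TEAE only at first onset, contrary to protocol 9.4.5, so on-treatment events that recur or worsen after the last dose are missing from the follow-up row of the study-period table

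*SAP*

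**What the plan says.** Protocol 9.4.5 sets a rule for counting AEs across study periods: "if a participant has multiple events with the same PT occurring in different periods, the event will be reported for each of those periods". Its one exception is a continuing event: "If an AE continues from one period to the next without increase in severity", the event stays in the period where it began. Under Assessment of Intensity in Protocol Appendix 4, when an AE becomes more severe "the increase in the severity will be recorded as a new AE and the original AE will stop when the new AE starts".

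SAP 10.2 describes two onset tables.

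- **Time of first onset.** This table uses week bands plus an After last dose category. Repeat occurrences count once, at the first. For participants who stop drug early, "all TEAEs occurring after treatment discontinuation will be reported in the" After last dose category.
- **Study period onset.** "The time of first onset will also be used to assign TEAEs by study period onset as follows": an Intervention Period, and a "Safety Follow-up Period (> Day 84 for intervention completers or > last dosing day for participants who discontinue intervention early"). The counting sentence is repeated: "If patients have multiple occurrences of a TEAE then it will be counted once for the first occurrence only". For early discontinuers, "TEAEs occurring after treatment discontinuation will be reported according to the time of first onset".

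SAP 10.2 treats AEs up to 14 days after the last dose as treatment-emergent and lists the study-period table among the planned incidence summaries. SAP 7.7 lists changes to the analysis sets, the time-dependent imputation, the tipping-point analysis and the PK set. It has no entry on AE counting.

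**The concern.** The two documents give different counts for the same table, and the SAP does not declare the change. The effect runs in one direction. The intervention period comes first, so first-occurrence counting leaves the Intervention row as it is and can only shrink the Safety Follow-up row.

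The participants lost are those whose event occurred on drug and then returned or worsened once drug was stopped. A reader of the table would take the follow-up row as the number of participants with that event in the follow-up period. Under the SAP rule it is the number whose first such event fell there. The rule is the same in every arm, but the loss need not be, because the share of recurrences can differ by arm.

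**Working it through.** No sample size, power or alpha figure is involved, and the plan states no figure to reproduce. The check compares the two rules and applies both to the same records.

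**Step 1: the rules side by side**

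| Situation (same participant, same PT) | Protocol 9.4.5 | SAP 10.2, study-period table |
|---|---|---|
| First onset after last dose | Follow-up | Follow-up |
| On treatment, continues into follow-up without worsening | Intervention only | Intervention only |
| On treatment, new onset in follow-up | Both periods | Intervention only |
| On treatment, worsens in follow-up (recorded as a new AE) | Both periods, since the exception covers only events that do not worsen | Intervention only, if the new record is treated as another occurrence of the same TEAE |

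The documents differ only in the last two rows.

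**Step 2: constructed example (assumed data).** All events are headache with separate onsets. Completers are given a last dose on Day 84, so that the Day 84 boundary and the last dose coincide.

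- A: completer, onsets Day 20 and Day 90 (90 − 84 = 6 days after last dose).
- B: completer, onset Day 91 only (91 − 84 = 7 days).
- C: last dose Day 40, onsets Day 10 and Day 45 (45 − 40 = 5 days).

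All three follow-up events lie within 14 days of the last dose, so they are TEAEs.

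| Row | Protocol rule | SAP rule |
|---|---|---|
| Intervention | 2 (A, C) | 2 (A, C) |
| Safety Follow-up | 3 (A, B, C) | 1 (B) |

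**Step 3: general form.** Let F be the follow-up count for a PT under the protocol rule, and r the share of those F participants who had the same PT on treatment. Then

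SAP follow-up count = F × (1 − r).

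In the example F = 3 and r = 2/3, so 3 × (1 − 2/3) = 1, as counted.

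The documents do not give r. Over the full range, with F = 10:

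| r (assumed) | Shown in follow-up row |
|---|---|
| 0 | 10 |
| 0.10 | 9 |
| 0.25 | 7.5 (average) |
| 0.50 | 5 |
| 0.75 | 2.5 (average) |
| 1 | 0 |

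**Step 4: what does not change.** SAP 10.2 already counts a participant once per SOC or PT in its incidence summaries, so overall, serious and special-interest incidence are the same under either rule. The listing of all AEs keeps every recurrence.

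**The case against.** The best case for the SAP is that the protocol leaves technical detail to it (9.4) and refers to it for the safety analyses (9.4.5). First-onset assignment is also a coherent rule for a table titled by onset. Safety analyses are descriptive, with no formal testing, and other outputs cover the period after drug: the After last dose category, the Marijuana Withdrawal Checklist summary (SAP 10.6.4) and the AE listings. For early discontinuers, the sentence placing all post-discontinuation TEAEs in After last dose may keep their recurrences visible in the other table.

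Much of this stands, and it limits the size of the point. It does not remove it. Adding detail is different from reversing a stated counting rule, and SAP 7.7 is where a reversal would be declared. The After last dose sentence directly follows the first-occurrence sentence, and the SAP does not say which one governs, so it cannot be relied on to recover the recurrences.

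A reader might infer three stronger things that the documents do not support:

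- **That events emerging after drug is stopped disappear, hiding withdrawal effects.** An event first seen after the last dose still enters the follow-up row. The protocol's description of the withdrawal checklist (8.3.7) does not link it to this table, and the checklist has its own summary.
- **That everyone with the same PT present in both periods is lost.** An event that continues without worsening belongs to its onset period under both documents.
- **That a particular number of percentage points is lost.** Nothing in the documents fixes the recurrence share, and the possible range includes zero.

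**Conclusion.** The point holds as an undeclared contradiction between SAP 10.2 and protocol 9.4.5, confined mainly to one descriptive table. As written, the SAP can understate the Safety Follow-up row and cannot overstate it. The loss is the fraction r of the protocol-rule count, from none at r = 0 to all at r = 1.

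This rests on two assumptions. First, a TEAE in the counting sentence means a PT, as in the protocol; the SAP does not say whether it means PT, SOC or both. Second, a worsening recorded as a new AE is treated as another occurrence of the same TEAE; if it were treated as a separate TEAE, only true recurrences would be lost.

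A secondary point is that SAP 10.2 is unclear on how first-occurrence counting combines with the After last dose rule for early discontinuers. The two onset tables may therefore disagree for those participants.

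**What to change.** In SAP 10.2:

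1. For the study-period table, replace the first-occurrence sentence with the protocol rule: count each participant once per PT in each period that has a new onset, or a worsening recorded as a new AE. Events that continue without worsening stay in their onset period. Change the early-discontinuer sentence for this table to match.
2. Keep first-occurrence counting for the time-of-first-onset table. State whether an early discontinuer's recurrence after the last dose is also counted under After last dose.

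The cost is one or two sentences and minor programming, with no new data. If the sponsor prefers first-onset counting, it should be declared and justified in SAP 7.7 and the table title should say that first occurrences only are shown. That closes the documentation gap but leaves recurrences out of the follow-up row.
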